7.8. IPSS Total Score

IPSS total score at Screening, Day 1, Weeks 4, 8, 12, and 24 (or early withdrawal) will be summarized by treatment and visit, including change from baseline.

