1.1. Synopsis

Protocol Title: A Phase 3 Double-Blind, Randomized, Placebo-Controlled, Multi-Center Study to Evaluate the Efficacy, Safety and Tolerability of Vibegron in Men with Overactive Bladder (OAB) Symptoms on Pharmacological Therapy for Benign Prostatic Hyperplasia (BPH)

Protocol Number: URO-901-3005

Brief Title: Vibegron in Men with BPH with OAB

Study Rationale: Beta-3 adrenergic receptor (β_3 -AR) agonists have shown efficacy (with improved safety relative to anticholinergics) in treating persistent OAB symptoms in men on BPH therapies. This subset of the broader OAB population setting has unique safety needs (eg, possibility of urinary retention) that have not been fully evaluated in previous clinical programs of OAB treatments. Study URO-901-3005 is designed to evaluate the safety, tolerability, and efficacy of vibegron (75 mg once daily [QD] administered for 24 weeks) or placebo in men with symptoms of OAB while receiving pharmacological therapy for BPH.

Objectives and Endpoints: The primary study objective is to assess the efficacy, safety, and tolerability of vibegron versus placebo in men with OAB symptoms on pharmacological therapy for BPH. The primary clinical efficacy hypothesis is that vibegron + BPH pharmacological therapy is more effective than placebo + BPH pharmacological therapy in reducing both a) the mean daily micturition episodes and b) mean daily urgency episodes, based on a 3-day diary. The safety hypothesis is that the vibegron + BPH pharmacological therapy is safe and tolerable in men with OAB symptoms and BPH.

Primary and secondary study endpoints are as follows: (Note “per day” refers to a continuous 24-hour period.)

Co-Primary Efficacy Endpoints

- Change from baseline (CFB) at Week 12 in the average number of micturition episodes per day
- CFB at Week 12 in the average number of urgency episodes (urgency: need to urinate immediately) per day

Secondary Efficacy Endpoints

- CFB at Week 12 in the average number of nocturia episodes per night
- CFB at Week 12 in the average number of urge urinary incontinence episodes per day for subjects with urinary incontinence at baseline

- CFB at Week 12 in the International Prostate Symptom Score (IPSS) Storage score (1-week recall)
- CFB at Week 12 in the average volume voided per micturition

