Secondary Efficacy 
 To assess the efficacy of vibegron compared with placebo in men with OAB symptoms on pharmacological therapy for BPH as defined by other key measures 	Secondary Efficacy 
 CFB at Week 12 in the average number of nocturia episodes per night CFB at Week 12 in the average number of urge urinary incontinence episodes per day for subjects with urinary incontinence at baseline CFB at Week 12 in the IPSS Storage score (1-week recall) CFB at Week 12 in the average volume voided per micturition
Safety 
 To assess the safety and tolerability of vibegron compared with placebo in men with OAB symptoms on pharmacological therapy for BPH 	Safety 
 AEs, concurrent medications, clinical laboratory, vital sign assessments, PVR volume, uroflow measures, IPSS, urodynamics (sub-study only)
Other Efficacy 	Other/Exploratory - Efficacy 
 CFB at Week 2, Week 4, Week 8, Week 16, Week 20 and Week 24 in the average number of micturition episodes per day CFB at Week 2, Week 4, Week 8, Week 16, Week 20, and Week 24 in the average number of urgency episodes per day CFB at Week 2, Week 4, Week 8, Week 16, Week 20 and Week 24 in the average number of nocturia episodes per night CFB at Week 4, Week 8, Week 20, and Week 24 in the IPSS Storage score (1-week recall) CFB at Week 4, Week 8, Week 12, Week 20, and Week 24 in the IPSS Quality of Life score (1-week recall) CFB at Week 4, Week 8, Week 12, Week 20, and Week 24 in the IPSS Voiding score (1-week recall) CFB at Week 2, Week 4, Week 8, Week 16, Week 20, and Week 24 in the average number of urge urinary incontinence episodes per day for subjects with urinary incontinence at baseline CFB at Week 2, Week 4, Week 8, Week 16, Week 20, and Week 24 in the average volume voided per micturition CFB at Week 2, Week 4, Week 8, Week 12, Week 16, Week 20, and Week 24 in the average number of total incontinence episodes per day for subjects with urinary incontinence at baseline

- Percent of all subjects with a 50% reduction from baseline in average urgency episodes (urgency: need to urinate immediately) per day at Week 2, Week 4, Week 8, Week 12, Week 16, Week 20, and Week 24

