1.1.2. Secondary Efficacy Objectives

Secondary Efficacy Objectives	Endpoints
To assess the efficacy of vibegron compared with placebo in men with OAB symptoms on pharmacological therapy for BPH as defined by other key measures	
 CFB to Week 12 in the average number of nocturia episodes per night CFB to Week 12 in the average number of urge urinary incontinence episodes per day for subjects with urinary incontinence at baseline CFB to Week 12 in the International Prostate Symptom Score (IPSS) Storage score (1-week recall) CFB to Week 12 in the average volume voided per micturition

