4.3.2. Patient Reporting Questionnaire Scoring

4.3.2.1. International Prostate Symptom Score

The International Prostate Symptom Score (IPSS) is based on the responses to 7 questions concerning urinary symptoms and 1 question concerning quality of life. Each question concerning urinary symptoms allows the subject to choose 1 out of 6 answers indicating increasing severity of the particular symptom. The responses are assigned points from 0 to 5. The total score can therefore range from 0 to 35 (asymptomatic to very symptomatic).

The questions refer to the following urinary symptoms:

Questions	Symptom	Subscale Category
1	Incomplete emptying	Voiding
2	Frequency	Storage
3	Intermittency	Voiding
4	Urgency	Storage
5	Weak Stream	Voiding
6	Straining	Voiding
7	Nocturia	Storage

Question 8 refers to the subject’s perceived quality of life (QoL). The answers to the single question to assess the quality of life this question range from “delighted” to “terrible” or 0 to 6.

Raw scores for each scale will be calculated as the sum of responses to all the questions within the scale, with missing values imputed as the average value over the scale if <50% of the scale items are missing. If $\geq 50\%$ of the items are missing, no scale score will be calculated, and the subscale score will be considered missing.

To transform the raw scores to a unified score ranging from 0 to 100, the following algorithms are used to derive the corresponding score at baseline, Week 12 and Week 24.

- For the Symptom Bother Score, the transformed score is:

$$score = \frac{(sum\ of\ actual\ score - lowest\ possible\ score)}{range} \times 100 = \frac{sum\ of\ actual\ score - 8}{40} \times 100$$

For Symptom Bother, higher scores correspond to the symptoms having a larger bother and lower scores represent a lower amount of bother due to symptoms.

- For the Coping, Concern, Sleep, Social Interaction, and Total HRQL Scores, the transformed score is:

$$score = \frac{(highest\ possible\ score - sum\ of\ actual\ score)}{range} \times 100$$

In this case, higher scores correspond to a higher quality of life and lower scores represent a lower quality of life.

[figure not shown]
4.3.2.3. [REDACTED]

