9. CHANGE FROM ANALYSIS PLANNED IN PROTOCOL

9.1. Exploratory endpoints

In protocol Section 3, the changes from baseline at Week 12 for the following endpoints are specified as other/exploratory endpoints. In addition, the CFB at Week 24 will be included.

- Symptom Bother Score as assessed by [REDACTED]
- HRQL total score as assessed by [REDACTED]

IPSS total score is included as an exploratory efficacy endpoint as well as a safety endpoint.

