14.2.6.1 Average Volume Voided per Micturition	FAS	Descriptive statistics, include CFB
14.2.6.2 Change from Baseline in Average Volume Voided per Micturition (MMRM)	FAS	Include all intervals but Week 12 in the front
14.2.6.3 Change from Baseline in Average Volume Voided per Micturition (MMRM)	PPS	Include all intervals but Week 12 in the front

Title	Population	Programming notes
Other Efficacy and PROs Endpoints		
14.2.7.1 International Prostate Symptom Score (IPSS) Quality of Life Score	FAS	Descriptive statistics, include CFB
14.2.7.2 International Prostate Symptom Score (IPSS) Voiding Score	FAS	Descriptive statistics, include CFB
14.2.8.1 Urgency Episodes per Day 50% Responder Analysis (CMH)	FAS	Descriptive statistics
14.2.9.1 Change from Baseline in Average Number of Total Incontinence Episodes per Day	FAS-I	Descriptive statistics, include CFB
14.2.9.2 Urge Urinary Incontinence Episodes per Day 75% Responder Analysis (CMH)	FAS-I	Descriptive statistics
14.2.10.1 Symptom Bother Score as Assessed by [REDACTED] (1-week recall)	FAS	Descriptive statistics, include CFB
14.2.10.2 Health-Related Quality of Life (HQOL) Subscale Coping Score as Assessed by [REDACTED] (1-week recall)	FAS	Descriptive statistics, include CFB
14.2.10.3 Health-Related Quality of Life (HQOL) Subscale Concern Score as Assessed by [REDACTED] (1-week recall)	FAS	Descriptive statistics, include CFB

Title	Population	Programming notes
14.2.10.4 Health-Related Quality of Life (HROL) Subscale Sleep Score as Assessed by [REDACTED] (1-week recall)	FAS	Descriptive statistics, include CFB
14.2.10.5 Health-Related Quality of Life (HRQL) Subscale Social Interaction Score as Assessed by [REDACTED] (1-week recall)	FAS	Descriptive statistics, include CFB
14.2.10.6 Health-Related Quality of Life (HRQL) Total Score as Assessed by [REDACTED] (1-week recall)	FAS	Descriptive statistics, include CFB
14.2.11.1 [REDACTED] Domains	FAS	Include 5 domain categorical summaries: mobility, self-care, usual activities, pain/discomfort and anxiety/depression
14.2.11.2 [REDACTED] Crosswalk Index Value	FAS	Descriptive statistics, include CFB
14.2.11.3 [REDACTED] VAS Value	FAS	Descriptive statistics, include CFB and percent CFB
14.2.12.1 Overall Symptom Severity Bladder Symptoms Based on Patient Global Impression of [REDACTED] (PGI [REDACTED])	FAS	Let's try to include both continuous variables (score and change from baseline) and categorical variable on the same table which will facilitate review

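### The only IPSS safety table reports the total score, in which a storage benefit can offset a voiding worsening, and no between-arm estimate is planned for the voiding score

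*SAP*

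**What the plan says.** Protocol section 3 (Objectives and Endpoints) includes IPSS among the safety endpoints without naming a score: "PVR volume, uroflow measures, IPSS, urodynamics (sub-study only". SAP 1.1.3 narrows this to the total. SAP 7.8 then states "IPSS total score at Screening, Day 1, Weeks 4, 8, 12, and 24 (or early withdrawal) will be summarized by treatment and visit". Changes since baseline are reported too, and Table 14.3.9.1 carries the summary on the SAF. SAP 9.1 gives the same number two roles: "IPSS total score is included as an exploratory efficacy endpoint as well as a safety endpoint".

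SAP 4.3.2.1 assigns each of the seven symptom items to a subscale. Items 1, 3, 5 and 6 (incomplete emptying, intermittency, weak stream, straining) are voiding. Items 2, 4 and 7 (frequency, urgency, nocturia) are storage. Change in the storage score at Week 12 is the third secondary efficacy endpoint (SAP 1.1.2 and 4.1.2), and SAP 1.2.3.2 sets superiority as the aim.

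The voiding score is planned as an exploratory efficacy endpoint. SAP 6.3.1 summarises it descriptively on the FAS at Weeks 4, 8, 12, 20 and 24, in Table 14.2.7.2, "International Prostate Symptom Score (IPSS) Voiding Score".

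**The concern.** The Protocol synopsis justifies the trial partly by this population's "unique safety needs (eg, possibility of urinary retention". For IPSS, the items that bear on that question are the voiding items. The safety section reports them only after adding the storage items, which the plan's own hypothesis moves the other way. If the drug works on storage, the IPSS safety table moves towards no harm whatever happens to voiding, and a flat or falling total is compatible with worse voiding.

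The two halves of the score are also analysed unequally. Storage gets an MMRM with a treatment difference and 95% CI (SAP 6.2). Voiding gets descriptive statistics only, although Protocol 9.4.2.2 says other change-from-baseline endpoints will use the same MMRM as urgency. SAP section 9, which lists changes from the protocol, does not record this one. PVR, urodynamics and uroflow (SAP 7.5 to 7.7) all get ANCOVA LS means with 95% CIs; SAP 7.8 has none. As planned, the report could not say with any stated precision how much patient-reported voiding symptoms differ between arms.

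**Working it through.** **1. The plan's own figure.** SAP 4.3.2.1 scores each item 0 to 5 and states: "The total score can therefore range from 0 to 35 (asymptomatic to very symptomatic".
- Voiding: 4 items x 5 = 20.
- Storage: 3 items x 5 = 15.
- Total: 20 + 15 = 35, which reproduces the stated range.

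**2. The offset.** Because the total is a sum, the vibegron-minus-placebo differences in mean change obey

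D(total) = D(storage) + D(voiding).

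Negative is improvement. This needs no assumption about variability. The documents give no IPSS effects, so the values below are assumed, to show the range:

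| Storage difference | Voiding +0.5: total shows | Voiding +1.0: total shows |
|---|---|---|
| 0 | +0.5 | +1.0 |
| -0.5 | 0 | +0.5 |
| -1.0 | -0.5 | 0 |
| -1.5 | -1.0 | -0.5 |

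The offset is complete only when the two differences are equal and opposite. With no storage effect there is none. With a larger storage effect the total looks like benefit.

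**3. What an interval on the voiding score would add.** Inputs: 462 per arm (SAP 1.2.4, evaluable at Week 12) and assumed SDs of change and correlations, since none are given. The formulas are:

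SD(total) = sqrt(SDv² + SDs² + 2 r SDv SDs)

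Half-width of the 95% CI = 1.96 x SD x sqrt(2/462)

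| SDv | SDs | r | SD(total) | Half-width, voiding | Half-width, total |
|---|---|---|---|---|---|
| 3 | 2.5 | 0.3 | 4.44 | 0.39 | 0.57 |
| 4 | 3 | 0.5 | 6.08 | 0.52 | 0.78 |
| 5 | 3.5 | 0.6 | 7.63 | 0.64 | 0.98 |

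For example, take the middle row, with an observed voiding difference of +1.0 and a storage difference of -1.0. The voiding interval is 1.0 ± 0.52, or 0.48 to 1.52. The interval for the total is 0 ± 0.78, or -0.78 to 0.78. The first shows a worsening; the second does not. Over the three rows the lower limit for voiding runs from 0.36 (1.0 - 0.64) to 0.61 (1.0 - 0.39). These half-widths ignore baseline adjustment.

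**The case against.** The strongest objection is that voiding harm is already well covered.
- The voiding score has its own by-visit table, so with the storage tables a reader sees both components.
- Protocol 8.3.5 names PVR as the proxy for impaired voiding. SAP 7.5 summarises it across visits with LS means, CIs and categories up to 300 mL and above.
- Uroflow has LS means and CIs, and the urodynamics sub-study was sized on noninferiority margins.
- Urinary retention is an adverse event of special interest, and Protocol 8.4.5 collects any worsening of BPH symptoms as an adverse event.

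All of this stands. It defeats the stronger conclusion a reader might draw, that the plan conceals voiding harm or that the drug's benefit necessarily cancels it.

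Two further points also stand. SAP 7.8 plans no test, so rejection probabilities for the total would describe an analysis nobody proposes. The FAS/SAF difference is probably small: the first post-baseline diary (Week 2) precedes the first post-baseline IPSS (Week 4), and under SAP 4.2.4.2 an earlier withdrawal IPSS would not be summarised by visit anyway.

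The objection does not supply the missing estimate. None of the other measures is a scheduled patient report of weak stream, straining, intermittency and incomplete emptying. A retention event requires catheterisation plus a PVR criterion (Protocol 8.4.6). SAP 7.7 places uroflow at Screening and Week 24 and summarises only voids of at least 125 mL. Urodynamics covers about 60 evaluable men. PVR measures volume, not symptoms. Adverse events rely mainly on open-ended questioning (Protocol 8.4.2).

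Reporting the total as a safety measure is itself a fair reading of the protocol, so it need not be removed.

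**Conclusion.** The point holds in a limited form. The IPSS safety table combines items expected to improve with items that could show harm, so it can understate a voiding worsening by the full size of any storage benefit. That follows from the scoring alone. The size of the offset in this trial is unknown; the differences, SDs and correlations used above are assumptions.

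The documents do not support reading this as a safety analysis that hides harm, nor as a contradiction in the plan. The gap is narrower: no between-arm difference or interval is planned for the patient-reported voiding score, in a trial whose rationale includes voiding safety. Closing it is a cheap improvement. Sample size, alpha and the primary and secondary analyses are unaffected.

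**What to change.** In SAP 1.1.3, 7.8 and Table 14.3.9.1, keep the IPSS total and add the IPSS Voiding score (items 1, 3, 5, 6) on the SAF beside it, by visit. Report the LS mean treatment difference and 95% CI from the SAP 4.2.2 ANCOVA, with treatment and baseline value as terms, as SAP 7.5 already does for PVR. Add a sentence that the total alone is not evidence on voiding safety, and cross-refer to Table 14.2.7.2. While editing, include Week 20: SAP 7.8 omits it, although IPSS is scheduled then and SAP 6.3.1 summarises it.

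The cost is wording and one extra table from data already collected and a score already derived. The downside is several nominal intervals with no multiplicity adjustment, which should be labelled as such. If the change is made after the SAP is final, SAP section 1 requires it to be documented in the clinical study report.

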8. COVID-19 CONSIDERATIONS

This study was conducted during the COVID-19 global pandemic (starting around March 2020). During the time period of the pandemic, it is anticipated that changes in study visit schedules, missed visits, or patient discontinuations may lead to missing information (e.g., for protocol-specified procedures). In accordance with the FDA Guidance titled Statistical Considerations for Clinical Trials During the COVID-19 Public Health Emergency (first issued in June 2020), it is important to capture specific information in the case report form that explains the basis of the missing data, including the relationship to COVID-19 for missing protocol-specified information (e.g., from missed study visits or study discontinuations due to COVID-19).

The proportion of subjects with COVID-19 impact on visits will be summarized by treatment group overall and by visit. The reasons (e.g. subject acquired COVID-19, subject unable to travel due to COVID-19, investigative site closure due to COVID-19, etc) will also be summarized. A listing of subjects who had COVID-19 information collected will be generated which will document the date of contact, visit, visit impact, reason for visit impact, and if any doses were missed due to IP availability.

9. CHANGE FROM ANALYSIS PLANNED IN PROTOCOL

9.1. Exploratory endpoints

In protocol Section 3, the changes from baseline at Week 12 for the following endpoints are specified as other/exploratory endpoints. In addition, the CFB at Week 24 will be included.

- Symptom Bother Score as assessed by [REDACTED]
- HRQL total score as assessed by [REDACTED]

IPSS total score is included as an exploratory efficacy endpoint as well as a safety endpoint.

9.2. Responder Analysis

Protocol Section 9.4.4 mentions using CMH risk difference estimate for response efficacy endpoints. Missing Week 12 data will be analyzed using multiple imputation (MI). Considering the responder endpoints are exploratory in the study, the proposed MI analysis will not be carried out.

9.3. COVID-19 Considerations

The COVID-19 global pandemic developed during the conduct of the study. The recommended impact analysis was therefore added to the SAP, as the operational change of increased visit windows had been initially communicated via study memo with no protocol amendment. COVID-19 expanded visit windows are spelled out in Protocol Amendment 2; 6-week visit extensions due to COVID-19 were available starting in March 2020.

11.1. Appendix 1. Multiple Imputation for the Response Efficacy Endpoints

This section summarizes the multiple imputation approach for the sensitivity analysis of primary efficacy endpoints to assess the robustness of the treatment effect under different underlying assumptions to account for missing data. The goal is to impute missing values as follows:

- Average number of daily micturition episodes
- Average number of daily urgency episodes

First the average daily numbers will be derived for all post-baseline visits as described in Section 4.3.1 respectively, then the following two-stage imputation will be applied. The following steps will be followed to perform this analysis.

Step 1: Create a horizontal dataset for the efficacy data where each patient has 1 row per parameter and a column for each visit from baseline through week 12, inclusive.

Step 2: Impute missing average daily numbers at Weeks 2, 4, and 8 based on MCMC to obtain a monotone missing data pattern with 30 replicates. Example code is:

```
proc mi data = datain1 out = dataout1 seed = 123 n impute=30 n o print;
  var baseline WEEK_02 WEEK_04 WEEK_08;
  mcmc chain = multiple impute=monotone;
  em maxiter = 1000;
run;
```

Step 3: For each of the 30 replicates from Stage 1, impute the missing data following a monotone missing data pattern so that there are 30 replicates of the complete dataset. Example code is:

```
proc mi data = dataout1 out = dataout2 seed = 321 n impute=1 n o print;
  class TRTP OABTYPE REGION ;
  monotone regression (WEEK_12 = baseline WEEK_02 WEEK_04 WEEK_08);
  var WEEK_12 baseline WEEK_02 WEEK_04 WEEK_08;
run;
```

Step 4: Transpose the dataset out2 to the usual ADaM-like dataset with 1 row per patient, per parameter, per analysis visit.

Step 5: Fit the ANCOVA model from Section 6.1.1 for each of the replicate complete datasets.

Step 6: Combine the results from Step 4 using PROC MIANALYZE.

```
proc mianalyze data = MIdatain;
  modeleffects ESTIMATE;
```

```
stderr STDERR;
ods output ParameterEstimates = MIout;
run;
```

The tipping point analysis will use the same approach and follow Example 80.13 from SAS/STAT User's Guide [8].

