7.2. Subject Discontinuation/Withdrawal from the Study

- Subjects who discontinue study drug will also withdraw from the study.
- A subject may choose to withdraw from the study at any time at his own request, or may be withdrawn at any time at the discretion of the investigator for safety, behavioral, compliance, or administrative reasons.
- If a subject withdraws consent for disclosure of future information, the Sponsor or designee may retain and continue to use any data collected before such a withdrawal of consent.
- If a subject withdraws from the study, he may request destruction of any blood or urine samples taken and not tested, and the investigator must document this in the site study records.
- Subjects who withdraw from the study will not be replaced (enrollment accounts for a predetermined dropout rate).

The Week 24/Early Withdrawal assessments will be completed when a subject withdraws or is withdrawn from the study, if possible (see Schedule of Assessments in [Section 1.3](#) and [Section 1.4](#)).

Reasons for discontinuation from the study include the following:

- AE
- Lack of efficacy
- Noncompliance
- Withdrawal of consent
- Lost to follow-up
- Physician decision
- Protocol deviation
- Death
- Screen failure
- Run-in Failure
- Other

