6.1. Co-Primary Endpoint Analysis

6.1.1. Primary Analysis

The primary analysis will be based on the FAS. Descriptive summary for observed and CFB will be provided by visit and treatment for both co-primary endpoints. Refer to parameter derivations from Bladder Diary data on Section 4.3.1.

Co-primary 1: CFB to Week 12 in average number of daily micturition episodes

For the assessment of difference between the treatment groups in change from baseline to Week 12 in average number of daily micturition episodes, a mixed model for repeated measures (MMRM) will be used incorporating on-treatment values at all time points (Weeks 2, 4, 8, 12, 16, 20, and 24). The model takes account of any correlation within the same subject over time by using all available data on the subjects. With the assumption of missing at random (MAR), this approach will provide unbiased estimates of treatment effects derived from the model.

The MMRM model will include terms for treatment, visit, baseline value (average number of daily micturition episodes), alpha blocker use with or without 5-ARI (with vs. without), baseline urinary incontinence (yes vs. no), region (US vs. non-US), and interaction of visit by treatment. Stratification factors as randomized will be used in the model. The Kenward-Roger adjustment will be used with restricted (or residual) maximum likelihood (REML) to make statistical inference. An unstructured covariance matrix will be used to model the correlation among repeated measurements. If the unstructured covariance model fails to converge with the default Newton-Raphson algorithm, the Fisher scoring algorithm will be used to provide initial values of the covariance parameters. In the rare event that none of the above methods yield convergence, the following structures will be investigated: heterogeneous Toeplitz, Toeplitz, heterogeneous First-Order Autoregressive [AR (1)], heterogeneous compound symmetry (HCS), and compound symmetry (CS). The covariance structure converging to the best fit, as determined by Akaike's information criterion (AIC), will be used.

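### The only imputation model given for the co-primary multiple-imputation check leaves out treatment arm, so the check does not match the MAR assumption of the primary analysis

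*SAP*

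**What the plan says.** SAP 6.1.2.2 (Analysis of Covariance with Multiple Imputed data) imputes every missing Week 12 value of the co-primary endpoints and refers to Appendix 11.1 for the method. The ANCOVA there contains treatment, baseline value, region and the stratification factors.

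Appendix 11.1 introduces its method with "The following steps will be followed to perform this analysis" and gives two PROC MI blocks, each labelled as example code:

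- Step 2 (MCMC, to reach a monotone pattern) uses "var baseline WEEK_02 WEEK_04 WEEK_08".
- Step 3 (Week 12) uses "monotone regression (WEEK_12 = baseline WEEK_02 WEEK_04 WEEK_08". Its CLASS line is "class TRTP OABTYPE REGION", but none of these three variables appears in the regression or in the VAR list.

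Neither block has a BY statement for treatment, and no prose names other imputation covariates. Step 5 reads "Fit the ANCOVA model from Section 6.1.1 for each of the replicate complete datasets", but Section 6.1.1 holds the MMRM; the ANCOVA is in 6.1.2.2. For the sensitivity shift, the appendix says: "The tipping point analysis will use the same approach and follow Example 80.13".

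For the primary MMRM, which contains treatment and treatment by visit, SAP 6.1.1 states: "With the assumption of missing at random (MAR), this approach will provide unbiased estimates of treatment effects derived from the model".

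**The concern.** An imputation model should contain the variable whose effect is then estimated. Without arm, a vibegron man and a placebo man with the same earlier diary values get Week 12 values from the same distribution. Imputed men then keep only the part of the treatment effect already visible in their earlier visits.

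This matters because Protocol 7.2 says "Subjects who discontinue study drug will also withdraw from the study". Men who leave early enough to have no valid diary day in the Week 12 window (Day 68–102, SAP 4.2.4.2) get their Week 12 value from this model. The MI ANCOVA and its tipping point are the planned missing-data checks on the co-primary result. An MI estimate that differs from the MMRM could be read as sensitivity to missing data when it comes only from an omitted covariate.

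A secondary point arises only if normality fails. The rank analysis in 6.1.2.2 is announced as using imputed Week 12 data, but its step 3 carries the last mid-rank forward for missing Week 12 values. After imputation none is missing.

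**Working it through.** **Design inputs (SAP 1.2.4).** 1:1 allocation, 544 per arm, 15% stopping before Week 12; micturition effect 0.46, SD 1.972; urgency effect 0.60, SD 2.811; two-sided 0.05. The documents give no figure for the MI analysis, so the design figures were reproduced first:

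- 544 × 0.85 = 462.4 evaluable per arm.
- Micturition: 0.46 / (1.972 × √(2/462)) = 3.55, power 94.3% (noncentral t). Stated: 94.3%.
- Urgency: 0.60 / (2.811 × √(2/462)) = 3.24, power 90.0%. Stated: about 90%.

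**Assumptions not in the documents.** Correlation r between visits, dropout timing, and the course of the effect over visits.

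**Formula.** Shrinkage = share missing × (1 − share of the effect kept in imputed men). With equal correlation r among baseline and visits, a constant effect and k post-baseline visits observed, share kept = k·r / (1 + k·r).

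| r | last visit Week 2 | Week 4 | Week 8 | mean kept | shrinkage at 15% missing |
|---|---|---|---|---|---|
| 0.3 | 0.23 | 0.38 | 0.47 | 0.36 | 0.15 × 0.64 = 9.6% |
| 0.5 | 0.33 | 0.50 | 0.60 | 0.48 | 0.15 × 0.52 = 7.8% |
| 0.8 | 0.44 | 0.62 | 0.71 | 0.59 | 0.15 × 0.41 = 6.2% |

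The pooled regression also absorbs some between-arm spread, which raises the mean kept slightly, to 0.379/0.490/0.596. For an effect growing 0.30/0.40/0.45/0.46 it is 0.290/0.375/0.455. Over both profiles:

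- 15% missing: 6.1–10.6%. Micturition is about 0.41–0.43 instead of 0.46, urgency about 0.54–0.56 instead of 0.60.
- 10% missing: 4.0–7.1%. This is nearer the FAS, which requires a post-baseline value. For example, if 5% of randomized men have none (assumed), 10/95 = 10.5% are imputed.
- Low edge: 1.9%, with 10% missing only the Week 12 diary and an adjacent-visit correlation of 0.8 that decays with lag.
- Ceiling: if imputed men keep none of the effect, shrinkage equals the share missing, 15%.

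With 1:1 arms and equal dropout, the shift is the same size in each arm: 0.46 × (1 − share kept)/2 = 0.09–0.16 micturitions/day. Imputed placebo men are drawn too good and imputed vibegron men too poor.

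**Simulation 1** (544 per arm, 30 imputations, Rubin's rules, 300 trials per case, 10 cases). At r = 0.5 and 15% missing, the estimate is 0.429 without arm and 0.465 with arm, 7.8% lower. The p<0.05 conclusion differed in 0 to 5 of 300 trials per case (0–1.7%).

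**Simulation 2** (500 trials, 5 imputations, 15% missing, constant effect).

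- Equal correlation 0.7, spread dropout: 0.442 against 0.451, 2% lower.
- Equal correlation 0.5, spread dropout: 0.430 against 0.453, 5% lower. This is close to the formula with baseline left out, k·r / (1 + (k−1)·r): mean kept (0.50 + 0.67 + 0.75)/3 = 0.64, shrinkage 5.4%.
- Adjacent correlation 0.5 decaying with lag, all leaving after Week 2: 0.391 against 0.460, 15% lower.

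**Waning effect.** Suppose the difference is 0.46 at Weeks 2–8 and zero at Week 12. Pooled imputation then gives 0.15 × 0.36 × 0.46 = 0.025 to 0.15 × 0.59 × 0.46 = 0.041 in vibegron's favour, where arm-specific MAR gives zero. In simulation, an early effect 1.6 times the Week 12 effect at equal correlation 0.7 gave a no-arm to with-arm ratio of 1.05.

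**Rank analysis.** The section title and the dataset name `rankmi` point to imputed data, which would make step 3 a leftover. The printed code instead keeps each man's last record, without limiting it to visits up to Week 12. The two rules cannot both apply.

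**The case against.** The strongest reply is that the code is only an example. It also omits BY processing that its own text requires: there is no BY for the 30 replicates, and nothing separates the two endpoints. The absence of BY TRTP therefore says little about what will be run, and TRTP in the CLASS line suggests that arm was intended. This stands as far as intent goes, so the shrinkage is conditional on the code being followed. It does not remove the gap, because no sentence in the SAP puts arm in the model.

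The consequences are also limited. This is a sensitivity analysis, FAS membership reduces the share imputed, and significance rarely changes. All of that is accepted.

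A reader might infer three stronger things that the documents do not support:

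- **That the bias is always conservative.** This needs an effect that is constant or growing to Week 12. The waning case above goes the other way.
- **That the reported tipping-point shift would be smaller.** The cited SAS example is not in the documents and the SAP does not say which arm is shifted. Only the starting point can be called unclear.
- **That omitting arm is a deliberate assumption of lost benefit after dropout.** Appendix 11.1 speaks of different underlying assumptions but declares none, and pooling moves both arms.

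**Conclusion.** The point holds, conditional on the printed code being followed. The co-primary MI check would then rest on an imputation model without arm, so it would be neither the MAR analysis assumed for the MMRM nor a stated alternative.

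For a constant or growing effect, expect shrinkage toward no difference of about 2–15% of the effect at up to 15% missing, and about 4–7% at roughly 10% missing. These sizes rest on assumed correlations, dropout timing and effect course. For a waning effect, a small bias in vibegron's favour is possible. No direction or size is claimed for the tipping-point shift.

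The primary MMRM, the hierarchical testing procedure and type I error are untouched. This should be corrected so that the missing-data checks can be interpreted; it does not threaten the main result. The rank-analysis conflict is secondary and arises only if normality fails.

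**What to change.** In Appendix 11.1:

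- Add TRTP as a predictor in both Step 2 and Step 3, or impute BY TRTP, preferably with the other ANCOVA covariates.
- List WEEK_12 last in VAR. With it first, a man who has baseline but no Week 12 value does not form a monotone pattern in that order.
- Point Step 5 to the ANCOVA in 6.1.2.2.
- State that the tipping point starts from this arm-inclusive model, and which arm is shifted.
- Declare any less favourable assumption about dropouts as a separate analysis.

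In 6.1.2.2, name one missing-data method for the rank analysis. One option is a rank ANCOVA at Week 12 within each imputed dataset, with results combined and the carry-forward step deleted. The other is carry-forward limited to visits up to Week 12, without the MI label; in that case remove `by avisitn` from the second PROC RANK so that all men are ranked together.

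Cost: a few lines of SAP text and code, and no new data.
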